10.3 Statistical Analysis Plan

10.3.1 Analyses of Focus Group Data.

Focus group discussions will be transcribed verbatim from the digital audio-recording, de-identified by assigning unique numerical codes, and entered into Dedoose software to assist with theme identification, coding textual data, and describing relationships among codes (via code co-occurrence and memoing functions). Following established focus group analysis guidelines, we will create a codebook of a priori and emergent themes including operational definitions of all codes and sample quotations to illustrate how to apply each code. Two study team members will then use the codebook to independently code the compiled user profiles while a third team member will review these sections of coded data and resolve discrepancies. We will draw a random sample of 20 instances for the coders to begin with and calculate an inter-rater reliability score based on their code assignments. If this score is <95%, we will refine the codebook definitions and retrain the coders. Coders will then complete the coding of the remaining instances and we will calculate an inter-rater reliability score. Discrepancies will then be reviewed and resolved by the research team. Coding and analytic activities will be discussed during weekly team meetings.

10.3.2 Primary Analyses for Usability Testing

A usability report will be compiled by Protocol Chair and reviewed by the investigator team and the AC. The report will include: a) a list of common problems like navigation problems; and b) recommended design-improvements that will be used in the final iterative stages of intervention adaptation.

10.3.3 Primary Analyses for RCT of YouTHrive

Stata version 15 (StataCorp) and SAS version 9.4 (SAS Institute) were used for power calculations and will be used for all analyses. The primary study outcome is HIV viral suppression at 5 months, measured as undetectable VL based on the standard level of detectability. The primary statistical test of intervention efficacy for YT will be the comparison between intervention and control arms of the proportion of participants with undetectable VLs at the 5-month follow-up, using a chi-square test. If there is evidence of baseline imbalance between intervention arms for important predictors of viral suppression, we will fit logistic regression models that adjust for those covariates.

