YLWH will be recruited from 8 SRVs (Bronx, Houston, Chicago, Philadelphia, Tampa, Atlanta, Raleigh/Durham/Chapel Hill, and Charlotte). Persons interested in the study will be screened to determine if they meet the eligibility criteria. Prospective participants can screen remotely or in person, and can be recruited within the SRV clinic or in the community, as long as they meet inclusion criteria. YLWH who meet all inclusion criteria will be invited for either an in-person or virtual enrollment visit. Screening and enrollment may also happen during one visit, when possible.

At the enrollment visit, participants will complete an in-office or online baseline CASI, complete a viral load test if one was not performed in the past 60 days, a urine screen for recent drug use, and will be randomized at survey outset to either intervention or control. The randomization sequence will be stratified by city and use random permuted blocks of size 2 and 4. YLWH assigned to the *YT* intervention will be shown example webpages of the intervention, will be given basic training on how to navigate the intervention, and will be given the opportunity to ask questions they have about the website. Control condition assigned participants will be shown example webpages they will receive during the intervention period.

The intervention period lasts five months. During this time, intervention participants will have continuous access to the *YT* website (mobile enhanced and available on all devices with internet connection). Participants in the control condition will receive an email with HIV-related information once per week.

Follow-up assessments will be conducted at the 5-month (i.e., immediate post-intervention; follow-up 1 in the clinical setting or online via a teleconferencing platform such as VSee or Zoom) time point. The 5-month follow-up visit will include an in-office or online administered CASI, a blood draw or self-administered finger prick to test for detectable viral load, and a urine screen for drug use. At the 5-month follow-up visit, up to 20 intervention participants will be offered additional compensation (as specified in each SRV's informed assent/consent form) to take part in an additional semi-structured interview with SRV staff or via Zoom with a member of the study team.

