3.3.3 RCT

At outset of the survey, participants will be randomized 1:1 to YT intervention or control group, based on a randomization sequence developed by the AC lead statistician and loaded into DFexplore via SAS. The randomization sequence will be stratified by city and use random permuted blocks of size 2 and 4.

SELECTION AND ENROLLMENT OF STUDY PARTICIPANTS

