6.2.2 Clinical Procedures

- Urine collection (in-person visits only)
- Blood collection or self-administered VL test (if no VL test result in medical chart within 60 days of enrollment date)

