10.3.4 Secondary Analyses for RCT of YouTHrive

As a secondary aim, we will investigate whether there is greater benefit from the YT intervention for substance-using participants compared with nonsubstance-using participants. We will use the same modeling approach described above to address this aim. First, we will examine the association between the intervention and viral detection separately among those who did and did not self-report current (since the last visit) substance use (i.e., yes/no for problematic alcohol use and/or illicit drug use). Second, to formally test whether there is an interaction between intervention arm and substance use, the models described above will be refit including an interaction term between substance use and intervention arm. Interactions will be evaluated on the additive scale. We will carefully examine the distribution of potential confounders of the substance use and VL association and adjust for them as necessary. As mentioned previously, we will adjust for covariates where appropriate.

The models described use logistic regression to model the outcomes. We will use estimates from these models to report prevalence differences and ratios. However, alternative (log-linear and Poisson) models may be explored to allow easy interpretation of parameters in the presence of common outcomes. In the event of loss-to-follow-up among study participants, we will perform sensitivity analyses of an alternative outcome. We will define an additional outcome where a failure is defined as either detectable VL or loss-to-follow-up. The analyses described above will be repeated with this alternative outcome. All of the models mentioned above can be modified to accommodate missing values in the outcome or covariates over time without dropping participants. Although attempts will be made to limit missing data, in the event that this occurs, we will carefully examine patterns of missingness. Multiple imputation will be implemented, as needed, to deal with missing covariate data.

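### The viral-load analysis in 10.3.3 prespecifies no adjustment for baseline viral load or city, and leaves the trigger, covariates and role of the adjusted model undefined

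*Combined protocol and SAP*

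**What the plan says.** - Section 10.3.3: "The primary statistical test of intervention efficacy for YT will be the comparison between intervention and control arms", made with a chi-square test on the proportion undetectable at 5 months. Adjustment is conditional: "If there is evidence of baseline imbalance between intervention arms for important predictors of viral suppression, we will fit logistic regression models". No threshold, covariate list or order of precedence between the two results is given.
- Section 3.3.3: "The randomization sequence will be stratified by city and use random permuted blocks of size 2 and 4".
- Section 6.2.2, at enrolment: "Blood collection or self-administered VL test (if no VL test result in medical chart within 60 days of enrollment date". Baseline VL is therefore a planned measurement, although the definition of enrolment in 5.1 does not require a completed result.
- Section 3.1: participants "will be randomized at survey outset to either intervention or control", so a VL specimen could post-date randomisation. Sections 5.1 and 5.3 place randomisation after the survey.
- Section 10.3.4 carries the same models forward: "the models described above will be refit including an interaction term between substance use and intervention arm". It also says "We will use estimates from these models to report prevalence differences and ratios" and "Multiple imputation will be implemented, as needed, to deal with missing covariate data". On covariates it adds only that adjustment will be made where appropriate.
- Sections 10.3.3 to 10.4 name neither baseline VL nor city as a covariate in any RCT analysis.

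**The concern.** The baseline value of an outcome is usually its best single predictor. Adjusting for it sharpens the arm comparison whether or not the arms happen to look unbalanced, because the gain comes from removing between-participant variation. A rule that adjusts only when imbalance is seen gives up that gain in every trial where it does not fire. Here one cannot tell how often it would fire, on which variables, or what would follow. An analyst would have to decide this after seeing the data.

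The documents give no power figure for VL, and 10.2.3 reports difficulty in obtaining VL measurements, so efficiency on this endpoint matters. The undefined covariates also pass into the substance-use interaction models of 10.3.4.

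**Working it through.** **The plan's own figure.** Section 10.2.3 powers self-reported adherence: SD 43, 240 analysed (120 per arm), two-sided 5%. Detectable difference = (1.96 + 0.84) × 43 × √(2/120) = 15.6 points, as stated. There is no VL counterpart to reproduce.

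**Inputs for VL.** From the documents: 1:1 allocation, 8 cities, permuted blocks of 2 and 4, and N = 240 (borrowed from the adherence calculation). Assumed: 50% suppressed at baseline; three sets of control-arm suppression at month 5 for those suppressed v unsuppressed at baseline (85/30, 80/40, 70/40); a 15-point overall effect as a common odds ratio; city SD 0.3 on the logit scale.

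**Hand check, 80/40.** Control rate = (0.80 + 0.40)/2 = 0.60; YT rate = 0.75. An odds ratio of 2.25 gives this, moving 80% to 90% and 40% to 60%.

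- Chi-square: null SE = √(2 × 0.675 × 0.325/120) = 0.0605; alternative SE = √((0.60 × 0.40 + 0.75 × 0.25)/120) = 0.0597. Power = Φ((0.15 − 1.96 × 0.0605)/0.0597) = Φ(0.53) = 70%.
- Adjusted for baseline VL: mean within-stratum variance is (0.16 + 0.24)/2 = 0.200 in control and (0.09 + 0.24)/2 = 0.165 in YT. The stratum effects of 10 and 20 points have variance 0.0025. Variance = 0.365/120 + 0.0025/240 = 0.00305; SE = 0.0552. Power = Φ(0.15/0.0552 − 1.96) = Φ(0.76), about 77.5%.

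**Simulation** (20,000 trials per cell; model with baseline VL and city, standardised risk difference, robust SE with a small-sample factor):

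| Control suppression | Chi-square | Prespecified model | Gain | Variance ratio | Equivalent N |
|---|---|---|---|---|---|
| 85/30 | 68.2% | 81.3% | 13.1 | 1.34 | 240 × 1.34 = 322 |
| 80/40 | 69.6% | 76.8% | 7.2 | 1.14 | 240 × 1.14 = 274 |
| 70/40 | 67.0% | 71.4% | 4.4 | 1.08 | 240 × 1.08 = 259 |

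**Sensitivity.**
- Share suppressed at baseline from 10% to 90% (effect 12 points where control suppression exceeds 75%): gain 2.0 to 13.1 points.
- Whole effect in those unsuppressed at entry: 8.7, 3.5 and 1.6 points in the three scenarios.
- All detectable at entry, log10 VL as covariate (odds ratio per SD 1.3, 1.6, 2.0): 61.5 to 64.2%, 62.2 to 66.3%, 63.1 to 69.3%, a gain of 2.7 to 6.2 points.
- City on top of baseline VL: 0.2 to 0.7 points at city SD 0.3, about 2 at SD 0.6.
- 20% of baseline VL missing, handled as a category: 79.1, 74.8 and 70.7%, against 68.0, 68.6 and 67.2% for the chi-square. Complete-case analysis gives 73.6, 67.1 and 61.7%, so the last two fall below the chi-square.
- Type I error: model 5.0 to 5.5% with the small-sample factor and 5.5 to 6.1% without; chi-square 4.3 to 5.2%.

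**What the imbalance rule recovers.** If the chi-square stays primary, nothing. If the triggered model replaces it, the p<0.05 rule gives 69.4, 70.1 and 67.3%. As shares of the gain these are 1.2/13.1 = 9%, 0.5/7.2 = 7% and 0.3/4.4 = 7%. Further runs cover looser triggers, in the same three scenarios (8,000 trials each) and in others with the effect set so that the chi-square has about 80% power (6,000 each):

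| Trigger on baseline VL | Share recovered, same scenarios | Share recovered, other scenarios |
|---|---|---|
| p<0.05 | 5–10% | 6–13% |
| p<0.10 | 11–18% | 17–22% |
| p<0.20 | 25–31% | 31–38% |
| Standardised difference >0.2 | 14–21% | 20–27% |
| Standardised difference >0.1 (fires in about 45%) | 44–54% | 56–65% |

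**The case against.** An unadjusted chi-square under randomisation is a legitimate primary test, so this is an efficiency choice and not an error. That stands, and the point claims no bias. Nor does the trigger inflate false positives: under the null, the triggered rules rejected in 3.0 to 3.7% of trials in the two scenarios run.

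The size rests wholly on assumed rates. The documents give no share suppressed at baseline, no association between baseline and month-5 VL, and no VL effect size. The 13-point gain needs a strong predictor. This also stands, and is why only a range is given.

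A reader might infer that the imbalance rule recovers almost none of the lost power. The documents do not support a statement that firm: with no trigger defined, its yield cannot be fixed, and a loose trigger recovers about half or more. A reader might also infer that the chi-square governs whenever the two results differ. Section 10.3.3 calls it the primary test but never says whether the triggered model replaces or supplements it.

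Section 10.3.4 allows covariates where appropriate, and its closing note refers to a Statistical Analysis Plan in which deviations are justified. If that is a separate document it might name covariates, but it is not available here, and the text of 10.3.3 stays open.

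Finally, 10.2.3 calls self-reported adherence the primary outcome. If that prevails, the point concerns a non-primary analysis.

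**Conclusion.** The point holds as a gap in prespecification with a cost in efficiency. The VL analysis names no baseline covariates, and the trigger, the covariates and the standing of the adjusted model are all undefined. With N = 240 and the assumed rates, prespecified adjustment is worth about 2 to 13 points of power, or about 3 to 6 if all participants are detectable at entry. Nearly all of it comes from baseline VL; city is included mainly so that the analysis follows the randomisation. The imbalance rule recovers between none and somewhat more than half of the gain, depending on a definition the plan does not give, and every version examined recovers less than prespecification. The change is worth making, but the documents do not support calling the planned test invalid or attaching a single figure to the loss.

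Which range applies depends on who is enrolled. Section 1.1 describes RCT participants as having detectable VL, while the objective in 2.1 is to sustain suppression and the Aim 3 criteria in 4.1 and 4.2 set no VL requirement. These passages must be reconciled.

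**What to change.** Before any outcomes by arm are seen, replace the last two sentences of 10.3.3 with the following, in substance:

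- The primary analysis of undetectable VL at 5 months is a logistic regression on arm, baseline VL and city, fitted whatever the baseline balance. It is reported as a standardised risk difference with a robust SE, which fits the prevalence differences already planned in 10.3.4.
- Baseline VL enters as detectable, undetectable or missing; if all participants are detectable, as log10 VL plus a missing indicator. Only specimens dated on or before randomisation count. Participants without a baseline VL are kept.
- Sparse cities are pooled by a rule set before unblinding.
- The imbalance trigger is deleted and the chi-square kept as a supportive analysis.
- The same covariates are used where 10.3.4 refits these models.

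A small-sample SE factor, an exact pooling cutoff and a Mantel-Haenszel fallback for non-convergence are optional SAP details.

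The cost is a protocol and SAP wording amendment with IRB review (11.4), a date check on baseline specimens and slightly more analysis work. No new data are needed. A baseline VL that is missing or up to 60 days old reduces the gain but does not bias the arm comparison. The documents do not show whether outcomes by arm have already been seen; this should be confirmed first. The conflict over the primary outcome (adherence in 10.2.3, VL in 10.3.3) must be settled separately; this change applies to the VL analysis.

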10.3.4 Secondary Analyses for RCT of YouTHrive

As a secondary aim, we will investigate whether there is greater benefit from the YT intervention for substance-using participants compared with nonsubstance-using participants. We will use the same modeling approach described above to address this aim. First, we will examine the association between the intervention and viral detection separately among those who did and did not self-report current (since the last visit) substance use (i.e., yes/no for problematic alcohol use and/or illicit drug use). Second, to formally test whether there is an interaction between intervention arm and substance use, the models described above will be refit including an interaction term between substance use and intervention arm. Interactions will be evaluated on the additive scale. We will carefully examine the distribution of potential confounders of the substance use and VL association and adjust for them as necessary. As mentioned previously, we will adjust for covariates where appropriate.

The models described use logistic regression to model the outcomes. We will use estimates from these models to report prevalence differences and ratios. However, alternative (log-linear and Poisson) models may be explored to allow easy interpretation of parameters in the presence of common outcomes. In the event of loss-to-follow-up among study participants, we will perform sensitivity analyses of an alternative outcome. We will define an additional outcome where a failure is defined as either detectable VL or loss-to-follow-up. The analyses described above will be repeated with this alternative outcome. All of the models mentioned above can be modified to accommodate missing values in the outcome or covariates over time without dropping participants. Although attempts will be made to limit missing data, in the event that this occurs, we will carefully examine patterns of missingness. Multiple imputation will be implemented, as needed, to deal with missing covariate data.

Finally, we will examine models that include covariates that quantify the degree of site usage and which components were used. The additional outcome of self-reported ART adherence will be examined. The outcome will be defined as the percentage of ART taken in the past 30 days. Differences in this proportion by study arm will be evaluated using the same approach as described above. To explore the effects of the YT intervention on the intermediate theory-based processes of change, we will use the IMB-AAQ informational and motivational scales, adherence self-efficacy, and social support measures at each time point. These scales will be included as outcome variables in linear regression models to test the main effect of intervention arm.

Note: Any deviations from the analysis plans outlined above or in the sections that follow will be documented and justified in the Statistical Analysis Plan developed for this protocol.

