YT	YouTHrive

STUDY ABSTRACT

DESIGN:	
YouTHrive (YT) is a two-arm randomized controlled trial (RCT) to test the efficacy of an adapted version of the Thrive With Me intervention for youth living with HIV (YLWH).

DURATION:	YLWH are enrolled for 5 months.
SAMPLE SIZE:	Total study sample is 368 of which the following will be enrolled for each aim: 1) 48 participants for focus groups to inform intervention adaption; 2) 12-20 participants for usability testing to finalize intervention components; 3) 300 participants for a randomized controlled trial of YT, with participants randomized to either YT (n=150) or control (n=150).
POPULATION:	Participants for all aims of the study will include YLWH inclusive of all genders and all races/ethnicities. Focus group participants will be recruited from SRVs in Bronx, Chicago, and Houston. Usability participants will be recruited from SRVs in Bronx, Chicago, Houston, Philadelphia, Tampa, and Atlanta. RCT participants will be recruited from SRVs in Bronx, Chicago, Houston, Philadelphia, Tampa, Atlanta, Raleigh/Durham/Chapel Hill and Charlotte area. Usability participants must have had a detectable VL in the past 12 months. RCT participants will be required to meet eligibility criteria.
STRATIFICATION:	Focus group discussions will be stratified by age (50% 15-19 yo; 50% 20-24 yo). We will stratify by SRV (i.e., city) site for the RCT.
DATA COLLECTION:	Focus group discussions will be conducted in-person, digitally recorded, and professionally transcribed. There will be three data collection (screening, baseline, and 5-month) time points for the RCT. Visits are conducted in-person at the SRV or remotely. Surveys will be completed using online survey tools (Alchemer and Qualtrics). VL measure collection will occur in-person at the participant's SRV or remotely. Urine screen will happen at in-person visits only. Process data of participant activity on YT and control interventions will include log-in activity, tasks completed on the website, and number of written posts.

OBJECTIVES:

- 1) In a 2-arm RCT (n=300), assess the efficacy of YouTHrive (YT) to sustain suppressed viral load (VL) among YLWH, compared to an HIV information-only control condition.
- 2) Assess whether YT is more beneficial for substance-using than non-substance-using YLWH.

INTRODUCTION

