1.2.3 RCT of *YT*

A 2-arm RCT of *YT* will be conducted, comparing the full version of the *YT* intervention to a control group. The control group will consist of weekly e-mails with a link to a webpage containing information about topics of interest to YLWH, but not addressing ART adherence. A RCT was chosen since it is the gold standard for assessing the effectiveness of an intervention under tightly controlled conditions. The intervention and control group will have access to intervention content for 5 months, with CASI performed at baseline and 5-month (i.e., immediate post intervention). VL will be assessed at baseline and 5- month time points to assess primary hypotheses (i.e., more participants in the *YT* group will have undetectable VL at the 5-month and assessment and, among those in *YT*, a greater proportion of substance-using participants will demonstrate sustained virally suppression than non-substance-using participants). Up to twenty purposively selected participants from the intervention group will also take part in a short, semi-structured interview over VSee or Zoom about their experiences on the site with study staff at their 5-month follow-up.

STUDY OBJECTIVES

2.1 **Primary Objective:** In a 2-arm RCT ($n=300$), assess the efficacy of YouT^hrive (*YT*) to sustain suppressed viral load (VL) among YLWH, compared to an HIV information-only control condition.

2.2 **Secondary Objective:** Assess whether YT is more beneficial for substance-using than non-substance-using YLWH.

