3.1 Study Phases/Aims

We will evaluate the *YT* intervention in a randomized controlled efficacy trial (see *YT* Schema) YLWH will be recruited from the 8 SRVs (Bronx, Houston, Chicago, Philadelphia, Tampa, Atlanta, Raleigh/Durham/Chapel Hill, and Charlotte), screened, and randomized to receive either the *YT* intervention or HIV-information only control condition. VL will be collected at the enrollment visit and 5-month follow-up assessment time point.

Phase/Aim 1: YT Intervention Adaptation

We will conduct six focus groups with approximately 8 youth (15-19 years old) and young adults (20-24 years old) each at 3 SRVs to obtain: 1) feedback from YLWH about the “look and feel” and content of the original *TWM* intervention; 2) suggestions for adapting the intervention for YLWH similar to themselves; 3) information about barriers to ART adherence and other challenges of living with HIV. Focus groups will be transcribed verbatim and a content analysis will be assisted by the Analytic Core (AC).

Phase/Aim 2: YT Adaptation and Build

Information and feedback gathered from the focus groups will inform the adaptation of the *TWM* intervention for YLWH. The ADAPT-ITT model will be used to guide the adaptation process. Briefly, the ADAPT-ITT model follows 8 steps- each contributing to the acronym; **A**sessment of target population needs and local resources; **D**ecision making on components to leverage and adapt from *TWM*; **A**daptation of components to target group and pre-testing; **P**roduction of intervention draft; **T**opical experts review adaptations; **I**ntegration of feedback leading to second draft; **T**raining for implementation; and **T**esting.

[name] and the research team will partner with Radiant Creative Group (RCG) in order to update the *TWM* intervention to include those features and functionality that arise during the aforementioned adaptation process. Usability testing with 12-20 participants at 6 SRVs (Bronx, Chicago, Houston, Philadelphia, Tampa, and Atlanta) will be conducted to finalize all features and components of the intervention (i.e., ensure that all features are working properly and function in a way that users can easily navigate).

Phase/Aim 3: Randomized Controlled Trial to Test Efficacy of YT

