10.4 Missing Data

Several procedures will be used to conduct data analysis when data for either outcomes or covariates are missing. The first step will be to assess the extent and pattern of missing data. If data are missing for only a few cases, then data analysis will be conducted only on study participants with complete data. However, when such a strategy would result in loss of data from a substantial proportion of participants, or if this approach would lead to biased or inaccurate results, then some form of imputation will be performed. The form of imputation used will depend on the nature of the data that are missing. For example, data that are collected repeatedly might be imputed using the “last value carried forward” method; and in some instances, interpolation between neighboring points might also be used.

When the primary endpoint is missing, one data analysis will be conducted using only cases with the endpoint. Subsequent analysis will be done where missing endpoints are imputed. Hot-deck imputation or regression imputation may also be used in this context.

HUMAN SUBJECTS

This study will be conducted in compliance with the protocol, ICH Good Clinical Practice (GCP) guidelines, and 45 CFR Part 46.

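### Section 10.3.4 does not say that the process scales are analysed at month 5 with baseline adjustment, and section 10.4 permits imputation methods that do not suit a single follow-up

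*Combined protocol and SAP*

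**What the plan says.** **Schedule.** The Study Abstract states: "There will be three data collection (screening, baseline, and 5-month) time points for the RCT". Section 1.2.3 places the computer-assisted surveys at baseline and month 5, and sections 6.2 and 6.3 schedule no other assessment. Viral load follows the same pattern (section 3.1): "VL will be collected at the enrollment visit and 5-month follow-up assessment time point". There is therefore one measurement after the intervention starts.

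**Analysis of the process scales (section 10.3.4).** To explore the theory-based processes, the plan takes the IMB-AAQ information and motivation scales, "adherence self-efficacy, and social support measures at each time point". It continues: "These scales will be included as outcome variables in linear regression models to test the main effect of intervention arm". No month-5 restriction, baseline covariate, arm-by-time term or within-person correlation is stated for these models. The same section says: "All of the models mentioned above can be modified to accommodate missing values in the outcome or covariates over time without dropping participants".

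**Missing data (section 10.4).** After a step that looks at the extent and pattern of missingness, the plan gives examples of imputation. One reads: "data that are collected repeatedly might be imputed using the “last value carried forward” method". The plan then offers a second option for such data: "in some instances, interpolation between neighboring points might also be used".

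**The concern.** The analysis text reads as if written for a trial with several follow-up visits. With only two survey points, two things go wrong.

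First, one of the points at which the process scales are to serve as outcomes is baseline, where the expected difference between arms is zero. Two analysts following section 10.3.4 could fit different models, one pooling both points and one using month 5 alone, and report estimates that differ twofold. In the pooled case a real effect on social support could be reported as absent.

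Second, the two methods that section 10.4 offers for repeated data have nothing suitable to work on. The only value before month 5 is baseline, and no value follows it. Last value carried forward would therefore assume no change in everyone lost to follow-up.

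**Working it through.** **Inputs from section 10.2.3.** 240 participants, taken as 120 per arm; type 1 error 5% (sidedness not stated, but two-sided reproduces the figures); social support SD 0.63, detectable difference 0.23; adherence SD 43, detectable difference 15.6 points; follow-up about 85%. **Assumed, not in the documents:** correlation ρ between baseline and month 5 of 0.3, 0.5 or 0.7, with equal SDs at both points.

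**1. The plan's own figures.** The detectable difference at one time point is (1.960 + 0.842) × SD × √(2/120).
- Social support: 2.802 × 0.63 × 0.1291 = 0.228 (stated 0.23).
- Adherence: 2.802 × 43 × 0.1291 = 15.55 (stated 15.6).

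Both reproduce as single-time-point comparisons. For 0.23 the noncentrality is 0.23/0.63 × √60 = 2.828, and power is Φ(2.828 − 1.960) = 80.7%.

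**2. Social support, both points pooled.** With no difference at baseline, the expected arm effect is (0 + 0.23)/2 = 0.115. The SD of a person's two-point mean is 0.63 × √((1+ρ)/2). The noncentrality becomes 2.828 × 0.5/√((1+ρ)/2).
- ρ = 0.3: 1.754, power 41.8%
- ρ = 0.5: 1.633, power 37.2%
- ρ = 0.7: 1.534, power 33.5%

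**3. Social support, separate models.** The month-5 comparison keeps 80.7%. The baseline model has expected effect zero, so it is only a balance check.

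**4. Social support, month 5 adjusted for baseline.** The residual SD is 0.63 × √(1−ρ²), so the noncentrality is 2.828/√(1−ρ²).
- ρ = 0.3: 2.965, power 84.2%
- ρ = 0.5: 3.265, power 90.4%
- ρ = 0.7: 3.960, power 97.7%

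**5. Last value carried forward at month 5.** Let a proportion m be missing in each arm. If those lost would have had the same average change as those seen, the expected effect is (1 − m) × the true effect.
- m = 15% (from 85% follow-up): 0.85 × 15.6 = 13.3 points
- m = 20% (from 240 of 300): 0.80 × 15.6 = 12.5 points

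Imputed values restore the sample size but do not make up for the dilution. With 300 randomised, 15% missing and SD 43, power is about 76% with carried-forward values and about 83% with complete cases.

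With unequal loss, let c be the average change in controls and d = 15.6. The expected estimate is (1 − m_YT)(c + d) − (1 − m_control)c.
- 10% missing in control, 20% in YT: c = −10 gives 0.80 × 5.6 + 0.90 × 10 = 13.5; c = +10 gives 0.80 × 25.6 − 0.90 × 10 = 11.5.
- 20% missing in control, 10% in YT: c = −10 gives 0.90 × 5.6 + 0.80 × 10 = 13.0; c = +10 gives 0.90 × 25.6 − 0.80 × 10 = 15.0.

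The size of the bias therefore depends on which arm loses more. The loss rates and values of c in this last step are assumptions.

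**6. Interpolation.** It needs a value on each side of the gap. Month 5 is the last visit, so it cannot be applied to a missing month-5 score.

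**The case against.** The strongest reply is that nothing in section 10.3.4 describes a pooled or averaged model. It speaks of regression models in the plural, and one model per time point fits the words as well. On that reading the month-5 estimate is not diluted and has the power stated in section 10.2.3. An unadjusted month-5 comparison is valid under randomisation, and section 10.3.4 already allows covariate adjustment where appropriate. This stands. A reader might infer that the plan definitely counts baseline as outcome and halves the effect, but the text does not go that far. The fault is that it leaves the choice open.

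Three further inferences are not supported.
- **That the time-point wording dilutes the adherence or viral-load result.** The sentence on main effects refers to the process scales. Self-reported adherence is dealt with earlier in section 10.3.4, without that wording, and the viral-load test in section 10.3.3 is fixed at month 5.
- **That last value carried forward is prescribed.** Section 10.4 introduces it as an example that might be used, after a review of missingness. For a missing primary endpoint it names a complete-case analysis, then hot-deck or regression imputation. Section 10.3.4 adds a sensitivity analysis that counts loss to follow-up as failure.
- **That the value carried forward is certainly pre-randomisation.** Sections 3.1 and 3.3.3 randomise at the start of the survey; sections 5.1 and 5.3 randomise after it. Only pre-intervention is safe.

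What remains is that neither reading of section 10.3.4 is a good specification, and that the two imputation examples do not fit the schedule, however tentatively they are offered.

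**Conclusion.** The concern holds as under-specification of the exploratory process-scale analyses, together with an unsuitable option in the missing-data section. For social support, the two readings of section 10.3.4 differ by a factor of two in the expected estimate, and power is about 81% under one and 33-42% under the other. Baseline adjustment at month 5 would give about 84-98%. The pooled and adjusted figures rest on the assumed correlations of 0.3 to 0.7; the 81% rests only on the plan's own inputs.

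The missing-data part reaches any survey score, including adherence, because section 10.4 covers outcomes generally. If last value carried forward were used, a true 15.6-point effect would be estimated at about 13.3-12.5 points under equal loss of 15-20%. Under unequal loss the bias depends on the pattern. The primary viral-load comparison at month 5 is not affected by the main-effect sentence. The change is worth making because it helps under either reading and uses data already collected.

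**What to change.** - **Section 10.3.4:** replace the reference to every time point with: the month-5 score is the outcome, with arm, baseline score and city as covariates. City belongs in the model because randomisation is stratified by it.
- **Section 10.4:** delete last value carried forward and interpolation for the RCT. Impute missing month-5 scale and adherence scores by multiple imputation, with arm and the baseline score in the imputation model. Section 10.3.4 already names multiple imputation for covariates, so this extends a method the plan has adopted.

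The cost is a change of wording in two sections. It needs no new data, visits or participants.
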